## 8 DEFINITIONS AND CONVENTIONS FOR DATA HANDLING

### 8.1 EFFICACY DATA HANDLING

#### 8.1.1 Baseline efficacy

All diary data prior to first dose date plus 6-week prior historical data at the time of enrollment will be used in the computation of baseline seizure frequency per 28 days. All subjects should have at least 6 weeks of diary data prior to baseline (Visit 2).

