#### 9.1.1 Screening Period (Week -6 ~ Week 0)

The Screening Visit (Visit 1) will take place no earlier than 6 weeks before the 1st dose of study drug. Seizure data from up to 12 weeks preceding 1st dose will be collected by the investigator, including retrospective data collection as needed. Subjects will be eligible for study enrollment after they have experienced either the 2 required unprovoked (or reflex) seizures or the 1 unprovoked (or reflex) seizure with EEG evidence of seizures, and they will not need to complete the full 12 week diary to enter the Titration Period. (revised per Amendment 01) Subjects without the required seizure data will fail screening, but may be rescreened 1 time. During the Screening Period, informed consent will be obtained and screening assessments will be conducted.

Before or at the Screening Visit (Visit 1), informed consent will be obtained after the study has been fully explained to each subject and before any baseline procedures or assessments are conducted. Procedures to be followed when obtaining informed consent are detailed in [Section 5.3](#).

Investigators will confirm the inclusion/exclusion criteria and will conduct the planned evaluations. Subjects should be no younger than 4 years of age and able to swallow perampanel tablets. They must have been diagnosed with epilepsy, consisting of POS with or without SGS or PGTCs. (revised per Amendment 01) Additionally, they must need monotherapy or they must need 1st adjunctive therapy with perampanel after failure to control seizures on monotherapy with another AED at the optimal dose and duration for that AED.

Screening results must be recorded on the appropriate electronic Case Report Form (eCRF) to indicate whether or not the subject is eligible to participate in the study and to provide reasons for screen failure if applicable. In addition, medical history, prior concomitant medications and prior concomitant AED of subjects will be obtained. Subjects who complete Visit 2 (Week 0) and meet all of the inclusion/exclusion criteria ([Section 9.3.1](#) and [Section 9.3.2](#)) will be enrolled and will begin the Titration Period.

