#### **9.5.1.1.3      SEIZURE TYPE AND FREQUENCY**

Seizure type and frequency/interval from the 12 weeks preceding the 1st perampanel dose (Visit 2) will be collected by the investigator, including retrospective data collection as needed.

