#### 4 DETERMINATION OF SAMPLE SIZE

The efficacy of perampanel as monotherapy and 1st adjunctive therapy for POS and PGTCs is to be evaluated. The primary endpoint is retention rate. The study is planned to enroll approximately 125 subjects. This sample size is considered adequate for an open-label Phase 4 study where there is no statistical hypothesis to be tested.

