## 5.4 Efficacy Analyses

This is a study without a control arm. Therefore, only descriptive statistics will be performed. The SAS will be used to summarize retention rate and the FAS will be used to summarize

seizure data.

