#### 5.4.3 Exploratory Efficacy Analyses

Analyses of exploratory efficacy endpoints will be performed in the subset of the FAS with sufficient baseline seizure frequency i.e. at least 1 seizure during the baseline. All summaries will be produced by seizure type (POS, SGS, and PGTCS).

For percent change in seizure frequency endpoints at each treatment Period [pre-treatment, treatment, (titration plus maintenance), maintenance and maintenance-LOCF], and for each seizure type:

- Mean, standard deviation, median, minimum, and maximum will be provided.

For responder rate endpoints at each time point (3, 6, 9, and 12 months in maintenance period, maintenance and maintenance-LOCF), and for each seizure type:

- Number and percentage of responders will be provided

95% confidence intervals for the percentage change and responder rate may also be calculated if allowed by the data.

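### Where qualifying seizures fall inside the baseline window, baseline frequency is biased upward, so the exploratory responder and percent-change results can look favourable without any drug effect.

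*SAP*

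**What the plan says.** **Entry.** Protocol 9.1.1 opens enrolment on seizures: "Subjects will be eligible for study enrollment after they have experienced either the 2 required unprovoked (or reflex) seizures", or one seizure with EEG evidence. It adds that "they will not need to complete the full 12 week diary to enter the Titration Period". A subject without the required seizure data fails screening and may be rescreened once. Protocol 9.1.2 lets Visit 2, the start of dosing, coincide with the Screening Visit. Inclusion criterion 2 (Protocol 9.3.1) gives no time limit for the qualifying seizures.

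**Data collected.** Protocol 9.5.1.1.3: "Seizure type and frequency/interval from the 12 weeks preceding the 1st perampanel dose (Visit 2) will be collected by the investigator", retrospectively where needed.

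**Baseline used.** SAP 8.1.1: "All diary data prior to first dose date plus 6-week prior historical data at the time of enrollment will be used". No seizure is excluded. The section then says that every subject should have at least 6 weeks of diary before Visit 2.

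**Analysis subset.** For the responder and percent-change endpoints, SAP 5.4.3 restricts the Full Analysis Set to subjects with "sufficient baseline seizure frequency i.e. at least 1 seizure during the baseline".

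**Comparator.** SAP 5.4: "This is a study without a control arm". Neither document mentions regression to the mean.

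**The concern.** Two selections push baseline the same way. First, the window can close shortly after the seizure that opened entry, and that seizure is counted. Second, the at-least-1 rule removes subjects whose baseline happened to be quiet and keeps those whose baseline happened to be busy. Follow-up over the 39-week Maintenance Period has neither selection, so measured frequency tends to fall back to the true rate even with an inert drug.

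The window length adds to this. A subject screened and dosed on the same day has only the 6 weeks of history, although the protocol collects 12 weeks. A single seizure then weighs twice as much in the rate.

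At stake are the 50% and 75% responder rates and the median percent change, which are the only planned measures of seizure reduction from baseline. Newly diagnosed subjects can qualify on one or two seizures, so low rates are plausible, and low rates are where the problem is largest.

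**Working it through.** **Plan's own figure.** There is none to reproduce. The documents state no baseline rate and no expected responder rate. "The study is planned to enroll approximately 125 subjects" is justified only by the absence of a hypothesis.

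**Inputs from the documents.** Entry after 1 or 2 seizures and no full diary needed (Protocol 9.1.1); 6 weeks of history plus diary (SAP 8.1.1); screening of at most 6 weeks (Protocol 9.1.1); at least 1 baseline seizure (SAP 5.4.3); 39 weeks = 273 days of Maintenance.

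**Assumptions.** Poisson seizures at the same rate before and after dosing; no drug effect; Maintenance completed; diary stops when the requirement is met. True rates of 0.5, 1 and 2 per 28 days are illustrative.

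**Step 1: the at-least-1 rule alone, fixed 12-week window.** Let μ = 3 × rate be the expected baseline count. Mean baseline divided by true rate is 1/(1 − e^−μ), which gives 1.29, 1.05 and 1.00. With baseline count b and Maintenance count M, a 50% responder needs M/9.75 ≤ 0.5 × b/3, that is M ≤ 1.625b. At 0.5 per 28 days, μ = 1.5 and M has mean 4.875:

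| b | P(b, given b ≥ 1) | M at most | P(responder) | Product |
|---|---|---|---|---|
| 1 | 0.431 | 1 | 0.045 | 0.019 |
| 2 | 0.323 | 3 | 0.283 | 0.091 |
| 3 | 0.162 | 4 | 0.463 | 0.075 |
| 4 | 0.061 | 6 | 0.780 | 0.047 |
| 5 | 0.018 | 8 | 0.940 | 0.017 |
| 6 or more | 0.006 | 9 or more | about 0.98 | 0.006 |

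The sum is about 0.255, or 26% after rounding. At 1 and 2 per 28 days the same calculation gives 13% and 5%.

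**Step 2: the plan as written, by simulation (200,000 subjects per setting).**

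| No drug effect, true rate per 28 days | 0.5 | 1 | 2 |
|---|---|---|---|
| Entry at 1 seizure: mean baseline ÷ true rate | 1.60 | 1.14 | 1.02 |
| 50% responders | 35% | 17% | 10% |
| Median change | −33% | +8% | +4% |
| Entry at 2 seizures: mean baseline ÷ true rate | 2.32 | 1.40 | 1.06 |
| 50% responders | 60% | 22% | 10% |
| 75% responders | 21% | 3% | 0.3% |
| Median change | −57% | −23% | +3% |

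At 2 per 28 days the mean baseline is nearly unbiased. The remaining 10% is mostly chance variation in a small count. If rates vary between subjects (gamma, shape 1, population means 0.5, 1 and 2, entry at 2 seizures), null 50% responders are 41%, 26% and 16%, with median change −41%, −23% and −10%.

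**Step 3: same entry rules, baseline over the fixed 12 weeks before first dose.** Null 50% responders fall to about 26%, 13% and 5% for one-seizure entry, and to about 42%, 16% and 5% for two-seizure entry. For one-seizure entry what remains equals Step 1, the at-least-1 rule alone.

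**Step 4: deleting the most recent seizure for everyone.** In a fixed 12-week window with no seizure-driven entry, mean baseline divided by true rate becomes (μ − 1 + e^−μ)/μ:

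- μ = 1.5: (0.5 + 0.223)/1.5 = 0.48
- μ = 3: (2 + 0.050)/3 = 0.68
- μ = 6: (5 + 0.002)/6 = 0.83

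That rule biases those subjects in the opposite direction.

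**The case against.** **Not every subject is affected by the entry rule.** Criterion 2 supports a diagnosis and has no time window. Adjunctive subjects have had 8 weeks of stable monotherapy and switch subjects are already treated, so their qualifying seizures may be old. This stands: a reader might infer that every baseline is inflated by the entry seizure, and the documents do not support that. Nor are these subjects free of bias, because the at-least-1 rule still applies to them.

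**SAP 8.1.1 asks for 6 weeks of diary.** If this were enforced, the window would be about 12 weeks and would not close at the seizure. But it conflicts with Protocol 9.1.1 and 9.1.2, which allow entry without a full diary and dosing at screening. Since screening starts at most 6 weeks before first dose, it could be met only by using the whole screening period. It limits the concern only if the texts are reconciled, and it leaves the at-least-1 selection in place.

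**Larger figures are tempting.** Adding one forced seizure to a 6-week window for everyone gives null 50% responders of 58%, 35% and 19%. Setting these against 26%, 13% and 5% suggests that the entry seizure adds 32, 22 and 14 points. That comparison changes window length and entry seizure together. At a constant 12 weeks the forced seizure gives 38%, 22% and 9%, a difference of 12, 9 and 4 points. The 6-week figures are an upper case, not the expected result of the plan.

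**The endpoints are exploratory and descriptive.** This is true and limits the priority. SAP section 7 also says enrolment stopped early and that there will be too few subjects for 95% CIs. A sensitivity analysis will therefore be imprecise, but the main percentages will also stand without intervals.

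**Conclusion.** The concern holds for the exploratory responder and percent-change endpoints. Where qualifying seizures fall inside the baseline window, the plan as written biases baseline upward. On the stated assumptions, null 50% responders are about 35%, 17% and 10% (one-seizure entry) or 60%, 22% and 10% (two-seizure entry) at 0.5, 1 and 2 seizures per 28 days. Subjects with older qualifying seizures have only the selection from the at-least-1 rule, about 26%, 13% and 5% with a 12-week window.

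The direction follows from the documents' rules. The size does not, because no seizure rate is given and the share of subjects with in-window qualifying seizures is unknown. The effect is large below about 1 per 28 days. With a common rate, the shift in mean baseline and median change is close to nil from about 2 per 28 days upward.

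A reader might infer that the trial's main results are compromised. They are not: retention and seizure freedom do not use baseline frequency. The change is worth making, but it is not critical.

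**What to change.** 1. **SAP 8.1.1:** compute baseline over the same fixed 12 weeks before first dose for every subject, combining the retrospective and prospective data that Protocol 9.5.1.1.3 already collects. Give a rule for subjects with incomplete 12-week history.
2. **SAP 8.1.1 against Protocol 9.1.1 and 9.1.2:** reconcile the 6-week diary statement with entry before the diary is complete and dosing at the Screening Visit.
3. **SAP 5.4.3, sensitivity analysis only:** repeat the responder and percent-change tables leaving out the qualifying seizure or seizures, only for subjects in whom they fall inside the baseline window. Do not delete the most recent seizure for everyone.
4. **Reporting:** state with both versions that, with no control arm and the at-least-1 rule, regression to the mean cannot be separated from drug effect. Neither version removes it fully.

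The cost is SAP wording and one extra run of exploratory tables, with no change to trial conduct. Qualifying seizures must be identifiable by date. The sensitivity subset will be smaller, because some subjects will have no other baseline seizure, and the responder figures will look less favourable.

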### 9.1.2 Titration Period

The Titration Period will begin with Visit 2, which may overlap with the Screening Visit (Visit 1), and will last for up to 13 weeks. (revised per Amendment 01) Subjects will receive perampanel tablets once daily (QD) before bedtime. The initial dose of perampanel 2 mg/day may be up-titrated in increments of 2 mg according to the investigator’s judgment, based on individual clinical response and tolerability, as shown in the following dosing schedule (Table 1):

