#### **9.5.1.2      Efficacy Assessments**

Exposure data will be utilized to assess the primary endpoint. Secondary efficacy variables will be based on seizure frequency. Seizure frequency data will be collected in subject diaries by subjects or guardian/legally authorized representative during the study including the Titration Period and the Maintenance Period. Baseline seizure frequency data for up to 12 weeks before Visit 2 (Week 0) will be collected by subjects or guardian/legally authorized representative, retrospectively (for history prior to screening) and prospectively (during baseline). Subjects will be eligible for study enrollment after they have experienced the 2 unprovoked (or reflex) seizures occurring greater than 24 hours apart, or 1 unprovoked (or

reflex) seizure with EEG evidence of seizures, and will not need to complete the full 12-week diary to enter the Titration Period. (revised per Amendment 01) Seizure frequency data in subject diaries will be reviewed with the investigator(s) at Visit 2, 4, 5, 6, and 7. Seizure frequency from diary entries or principal investigator verification will be used to assess efficacy endpoints as appropriate. (revised per Amendment 01)

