## 7 CHANGES IN THE PLANNED ANALYSES

Due to recruitment challenges, enrollment was terminated before reaching the planned sample size. Thus, there will not be enough sample size to calculate the 95% CIs. Analysis of BDI-II scale is added as an exploratory analysis.

There are no other changes to the analysis in this statistical analysis plan compared to the protocol. Any future changes to the analysis will be documented separately and will be addressed in the Clinical Study Report.

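### The SAP's baseline seizure window reaches 12 weeks only with a 6-week pre-dose diary, which the protocol does not require

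*SAP*

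**What the plan says.** SAP 8.1.1 builds the baseline frequency per 28 days from two pieces: "All diary data prior to first dose date plus 6-week prior historical data at the time of enrollment". Its second sentence states the premise: "All subjects should have at least 6 weeks of diary data prior to baseline (Visit 2". Six weeks of diary plus six of history make 12 weeks.

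Protocol 9.5.1.1.3 sets the collection window: "Seizure type and frequency/interval from the 12 weeks preceding the 1st perampanel dose (Visit 2) will be collected by the investigator", with retrospective collection as needed. Protocol 9.5.1.2 is softer: "Baseline seizure frequency data for up to 12 weeks before Visit 2 (Week 0) will be collected". Protocol 9.1.1 and Table 4 footnote a also put 12 weeks as an upper limit, and footnote o makes retrospective history conditional on availability.

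On screening length, Protocol 9.1.1 says "The Screening Visit (Visit 1) will take place no earlier than 6 weeks before the 1st dose of study drug", so a prospective screening diary cannot exceed 6 weeks. There is no lower limit. Protocol 9.1.2 lets Visit 2 overlap Visit 1, and 9.1.1 lets subjects enter titration without the full diary.

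SAP 5.4.3 restricts the exploratory seizure analyses to subjects with at least one baseline seizure. SAP 7 lists the dropped confidence intervals and the added BDI-II analysis, and then states: "There are no other changes to the analysis in this statistical analysis plan compared to the protocol".

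**The concern.** The SAP rule rests on a diary length that the protocol does not require, and the SAP does not say what to do when the diary is shorter. On the natural reading, in which diary data are prospective and historical data are recalled, baseline length then depends on how quickly a site moves from screening to first dose. A subject dosed on the day of screening is judged on 6 weeks even when 12 weeks of history are on file.

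Two things follow for the responder rates and the percent change. A shorter window leaves more subjects with no baseline seizure, and they are excluded. Among those kept, requiring at least one seizure in a short window pushes the baseline rate up, so a return to the subject's usual rate looks like improvement. With no control arm, nothing offsets this. Low rates are plausible here, because eligibility needs only two seizures, or one with EEG evidence. Enrollment also stopped early, so avoidable exclusions cost more.

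**Working it through.** Neither document gives a responder rate, seizure rate or screening-length distribution, so there is no plan figure to reproduce. Seizure rates below are assumptions, shown as a range.

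**Step 1: window length.** With D weeks of prospective diary (0 to 6), the SAP baseline is 6 + D weeks, and the share of a full 12-week history left unused is 1 − (6 + D)/12.

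| D (weeks) | SAP baseline (weeks) | Unused share |
|---|---|---|
| 0 | 6 | 50% |
| 2 | 8 | 33% |
| 4 | 10 | 17% |
| 6 | 12 | 0% |

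**Step 2: one subject.** One seizure, falling in the last 6 of 12 weeks, scores 4 × 1/6 = 0.67 per 28 days on the 6-week window and 4 × 1/12 = 0.33 on the 12-week window. Over 39 weeks of Maintenance, a 50% response allows at most 0.5 × (1/6) × 39 = 3.25 seizures, so 3, with the 6-week baseline. With the 12-week baseline it allows 0.5 × (1/12) × 39 = 1.63, so 1. An unchanged rate of 1 per 12 weeks produces 39/12 = 3.25 seizures on average.

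**Step 3: no-effect responder rate.** Let r be the rate per 12 weeks, the same before and during treatment, and w the baseline length in weeks. The baseline count B is Poisson with mean r·w/12. The Maintenance count F is Poisson with mean r·39/12. The 50% responder rate is the sum over b ≥ 1 of P(B = b | B ≥ 1) × P(F ≤ 0.5 × 39 × b/w). For 75% responders, 0.25 replaces 0.5. The usable share is 1 − exp(−r·w/12).

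For r = 1 and w = 6, the terms for b = 1 to 5 are:
- b = 1: 0.7707 × 0.5914 = 0.456
- b = 2: 0.1927 × 0.9523 = 0.184
- b = 3: 0.032
- b = 4: 0.004
- b = 5: 0.0004

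Their total is 0.676. For w = 12 the same sum gives 0.372.

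Same-day dosing with full history, 6-week against 12-week baseline:

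| Seizures per 12 weeks | 50% responders | Usable baseline |
|---|---|---|
| 1 | 67.6% vs 37.2% | 39% vs 63% |
| 2 | 33.3% vs 19.1% | 63% vs 86% |
| 3 | 20.9% vs 12.9% | 78% vs 95% |
| 4 | 15.6% vs 9.5% | 86% vs 98% |
| 12 | 3.2% vs 1.1% | 99.8% vs about 100% |

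At 1 per 12 weeks, 75% responders are 27.0% against 12.5%. With two weeks of screening (8-week baseline), 50% responders at that rate are 50.2% against 37.2%.

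**Step 4: sensitivity.**
- Rates varying between subjects (gamma, mean 1 per 28 days; 400,000 simulated subjects): 50% responders 27.4% against 19.0%, exclusions 40.1% against 25.1%, median percent change −23% against −8% with no effect.
- The same with added within-subject overdispersion: 50% responders 41.5% against 30.1%, exclusions 51.8% against 32.2%.
- 13 weeks of follow-up at 1 per 28 days: 35.4% against 24.3%.

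The 6-against-12-week direction held wherever the rates were not negligible. For intermediate windows with short follow-up, the discreteness of counts can reverse it slightly. At 0.25 per 28 days and 13 weeks of follow-up, an 8-week baseline gives 53.2% and a 12-week baseline 56.4%.

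**The case against.** The strongest reply is that the two sentences of SAP 8.1.1 belong together. Read together they aim at 6 + 6 = 12 weeks, the protocol's own window, and lose nothing when the premise holds. That stands. A reader might infer that the SAP deliberately discards half of the collected data; the text does not support this. What fails is the premise, because the protocol does not require the diary.

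The word diary is also ambiguous. The protocol speaks of a 12-week diary although screening lasts at most 6 weeks, so retrospective entries may count as diary. On that reading the loss shrinks or disappears. On another reading, with the six weeks of history counted back from Visit 2, history overlaps diary and even a full screening yields only 6 weeks. The ambiguity tempers the claim, but it also means two programmers could derive different baselines.

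A reader might further call this an undeclared change from the protocol, given SAP 7. That is not established. The protocol fixes what is collected, mostly as up to 12 weeks and if available, but never defines the baseline window for analysis. It leaves the details to the SAP, which may simply be filling that gap.

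Finally, the affected endpoints are exploratory and descriptive. Retention, seizure freedom and conversion to monotherapy do not use this baseline.

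**Conclusion.** The point holds as a mismatch between SAP 8.1.1 and the screening rules in Protocol 9.1.1 and 9.1.2, with a bias of known direction in the exploratory responder and percent-change results. If diary means prospective entries, subjects with less than 6 weeks of screening get a baseline of 6 + D weeks and lose up to half of the history available for them.

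The size rests on the assumed rate, no drug effect, same-day dosing and a full 12-week history. Under those conditions the excess in 50% responders runs from about 30 percentage points at 1 seizure per 12 weeks, through 14 at 2 and 6 at 4, to 2 at 12. It would be wrong to read the 30 points as the expected inflation in this trial: it belongs to the lowest rate tabulated and the shortest screening, and the documents give neither the seizure rates nor the share of subjects dosed early. After 6 weeks of screening the effect is nil. The amendment is worth making because it is cheap and removes a dependence on site speed, but the primary and secondary results do not turn on it.

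**What to change.** Replace both sentences of SAP 8.1.1 with:

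*Baseline seizure frequency per 28 days = 28 × (seizures recorded, retrospectively or by diary, from Day −84 to Day −1) / (days in that span with seizure information), each calendar day counted once.*

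Delete the 6-week diary expectation or reconcile it with Protocol 9.1.1 and 9.1.2; changing only the first sentence would leave the contradiction in place. Report the distribution of baseline length.

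The cost is one derivation rule and its programming, with no new data. There are two downsides. More of the baseline rests on recall in subjects with short screening. For adjunctive subjects, some days may also precede the 8-week period of stable AED dosing. If the window is capped for that reason, use every collected day inside the cap and state the cap in the SAP.
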